Study 1: Exploratory study - identifying the benefits of pMDI versus Diskus for delivering fluticasone/salmeterol combination therapy in patients with chronic obstructive pulmonary disease (COPD)

Version Date: 7 February 2014

Protocol

**Study 1: Exploratory study -
identifying the benefits of pMDI
versus Diskus for delivering
fluticasone/salmeterol combination
therapy in patients with chronic
obstructive pulmonary disease
(COPD)**

To characterise patients with COPD initiating with fluticasone/salmeterol combination therapy via pMDI and Diskus and to identify and compare the potential benefits of using either device in the delivery of fluticasone/salmeterol combination therapy

Contents

OBJECTIVES	3
BACKGROUND	3
DATASOURCE	4
STUDY DESIGN	4
STUDY OUTCOMES	7
STATISTICAL ANALYSIS.....	8
TIMELINE, DELIVERY AND COSTINGS	9
RESEARCH TEAM	9
REFERENCES.....	9

OBJECTIVES

The aims of this exploratory study are to characterise patients with chronic obstructive pulmonary diseaseⁱ (COPD) initiating with fluticasone/salmeterol combination therapy delivered via pressurised metered dose inhaler (pMDI; also known as Evohaler) or Diskus (also known as Accuhaler); and to identify and compare the potential benefits of using either device in the delivery of fluticasone/salmeterol combination therapy.

This will be carried out by:

- (1) Characterising patients with COPD on fluticasone/salmeterol combination therapy via pMDI and Diskus.
- (2) Identifying and comparing the potential benefits of using pMDI versus Diskus in the delivery of fluticasone/salmeterol combination therapy in terms of both efficacy and adverse events, in particular:
 - a. Number of COPD exacerbations
 - b. Development of pneumonia infections
 - c. Type II diabetes diagnosis
 - d. Therapeutic indexⁱⁱ
 - e. Number of severe COPD-related events, including:
 - i. Lower respiratory tract infections
 - ii. Oral thrush

These are more clearly defined under 'Dataset Variables' below.

BACKGROUND

Inhaled corticosteroid use by patients with obstructive lung disease is associated with increased risk of pneumonia [1], increased risk of developing type-II diabetes [2] and increased risk of oral thrush [3].

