- Development of pneumonia (recorded as absence/presence of, and confirmed via: chest X-ray within a month of a pneumonia diagnosis OR hospitalisation within a month of a pneumonia diagnosis). Note that baseline values will be zero due to study exclusion criteria.
- Development/progression of diabetes
 - Development of diabetes (recorded as absence or presence of) during outcome period for patients (for patients without diabetes at or prior to IPD)
 - Progression of ongoing type-II diabetes treatment to insulin (defined as no insulin prescription during 1 year baseline period AND any insulin prescriptions during 1 year outcome period)
 - Diabetic control (defined as change in HbA1c value prior to starting Seretide® and after IPD)
 - Diabetic medication (defined as change in anti-type-II diabetic medication dosage OR medication type)
- Number of potential severe COPD-related adverse events and date of event including
 - Oral thrush
 - Lower respiratory tract infections
 - Bronchitis
 - Dysphonia / hoarseness
 - Nasopharyngitis (common cold)
 - Sinusitis
 - Hypokalemia (low blood potassium)
 - Muscle or joint pain
- ICS dose (in outcome period only) and date of ICS prescription

Matching will be used if required.

STUDY OUTCOMES

The primary aim of the current study is to identify baseline and outcome characteristics of patients with COPD initiating with Seretide® combination therapy via pMDI and Diskus and to identify and compare the potential benefits of using each device in the delivery of Seretide®. Among other events, the effect of device on the following outcomes will be investigated:

(1) COPD related severe exacerbations

Where an exacerbation is defined as an occurrence^{vii} of:

- COPD-related: Unscheduled hospital admission / A&E attendance^{viii}; OR
- An acute course of oral steroids prescribed with evidence of a respiratory review^{ix};
OR

-
- b) Asthma/COPD review codes excl. any monitoring letter codes;
 - c) Lung function and/or asthma monitoring.

^{vii}Where ≥ 1 oral steroid course / hospitalisation / antibiotics prescription occur within 2 weeks of each other, these events will be considered to be the result of the same exacerbation (and will only be counted once).

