^{viii}**COPD-related Hospitalisations:** consist of either a definite COPD Emergency Attendance or a definite COPD Hospital Admission; OR a generic hospitalisation read code which has been recorded on the same day as a **Lower Respiratory Consultation*** (see below - excluding where the only lower respiratory code recorded on that day was for a lung function test).

^{ix}**Evidence of a Respiratory Review** - consists of the following:

- Antibiotics prescribed with evidence of a respiratory review^{ix}.

(2) COPD related adverse events

Where adverse events include the number of incidences of:

- Oral thrush
- Lower respiratory tract infections
- Bronchitis
- Dysphonia / hoarseness
- Nasopharyngitis (common cold)
- Sinusitis
- Hypokalemia (low blood potassium)
- Muscle or joint pain

(3) Therapeutic index

Therapeutic index = highest dose not causing harm (side effect) / lowest dose that causes benefit (reduced number of severe COPD-related events).

For the highest dose not causing harm: the median dose at which no (any) adverse events occur

For the lowest dose that causes benefit (reduced number of severe COPD-related events): median dose at which patients show no increase in number of exacerbations in outcome

STATISTICAL ANALYSIS

Statistically significant results will be defined as $p < 0.05$ and trends as $0.05 \leq p < 0.10$

Summary statistics will be produced for all baseline and outcome variables, as a complete dataset and by device. For variables measured on the interval or ratio scale, these will include:

Sample size (n) & percentage non-missing

Mean & Variance / Standard Deviation

Range (Minimum / Maximum)

Median & Inter-quartile Range (25th and 75th percentiles)

For categorical variables, the summary statistics will include:

Sample size (n)

Range (if applicable)

Count and Percentage by category (distribution)

Treatment arms will be compared using t-test / Mann Whitney U-test (depending on distribution) for variables measured on the interval/ratio scale and using a chi square test for categorical variables.

a) Any **Lower Respiratory Consultation*** (see below) and

b) Any additional respiratory examinations, referrals, chest x-rays, or events.

* **Lower Respiratory Consultations** - consist of the following:

a) Lower Respiratory read codes (including Asthma, COPD and LRTI read codes);

b) Asthma/COPD review codes excl. any monitoring letter codes;

c) Lung function and/or asthma monitoring.

TIMELINE, DELIVERY AND COSTINGS

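### The therapeutic index's harm term omits pneumonia and diabetes, and an antibiotic-treated LRTI can enter both its harm and its benefit term

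*Protocol*

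**What the plan says.** Study Outcomes numbers three outcomes.

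- Outcome (1) is "COPD related severe exacerbations". One of its three routes is "Antibiotics prescribed with evidence of a respiratory review". The footnotes define a respiratory review as (a) a lower respiratory consultation and (b) "Any additional respiratory examinations, referrals, chest x-rays, or events". The consultation itself covers "Lower Respiratory read codes (including Asthma, COPD and LRTI read codes".
- Outcome (2) is adverse events: "Where adverse events include the number of incidences of" eight items, among them "Lower respiratory tract infections" and bronchitis. The other six are oral thrush, dysphonia, common cold, sinusitis, hypokalaemia, and muscle or joint pain.
- Outcome (3) is the therapeutic index. Its numerator is the median dose where no adverse event of any kind occurs. Its denominator is the median dose among patients whose exacerbation count does not rise in the outcome year.

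Pneumonia and type II diabetes appear elsewhere. The Background names both as risks of inhaled corticosteroids, Objectives 2b and 2c make both part of the comparison of efficacy and adverse events, and Dataset Variables defines confirmed pneumonia and several diabetes measures. There they stand as separate entries beside the adverse-event list, not inside it.

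Objective 2e adds "Number of severe COPD-related events, including" LRTI and oral thrush.

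**The concern.** The index is the one place where the study sets benefit against harm. If its harm term ignores two of the three corticosteroid risks that the Background gives as the reason for looking at harm, while it counts colds and joint pain, the index answers a different question from the one in the Objectives.

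The overlap is a second, smaller problem. When one infection can be scored as lost benefit and as harm, the two terms of the ratio are partly driven by the same episodes. A device difference in LRTI could then move both terms, and a reader could take one signal for two.

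**Working it through.** The protocol states no event rate, effect size or sample size, so there is no figure to reproduce. The check sets the definitions side by side.

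**Is pneumonia or diabetes in the harm term?**

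1. The harm term calls on any adverse event. The only adverse-event lists are in Dataset Variables and Study Outcomes (2), and they hold the same eight items.
2. Items that are pneumonia: 0 of 8. Items that are diabetes: 0 of 8. Neither appears in any of the three numbered outcomes.
3. Of the three risks named in the Background (pneumonia, diabetes, oral thrush), 1 of 3 reaches the list.
4. Take a patient with X-ray-confirmed pneumonia or newly recorded diabetes in the outcome year and none of the eight items. That patient stays in the group over which the harm-free median dose is taken. If such patients tend to be on higher doses, the numerator is raised; the document does not allow the size or the direction to be computed.
5. The data are to hand. Pneumonia in the baseline year is an exclusion, so outcome-year pneumonia has a zero baseline. New diabetes is derived for patients without it at or before the index date, and progression to insulin is derived for those on treatment.

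**Can one episode enter both terms?**

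1. Start with an LRTI read code and an antibiotic prescription.
2. The LRTI code is a lower respiratory consultation, which is limb (a) of a respiratory review.
3. If (a) and (b) are a list of qualifying evidence, the review is established and the episode is an exacerbation. If both limbs are required, it is an exacerbation only when a further examination, referral, chest X-ray or event is recorded.
4. The same LRTI is an item in outcome (2).
5. The two-week rule merges steroid courses, hospitalisations and antibiotic prescriptions into one exacerbation. It says nothing about an exacerbation and an adverse event.
6. In the index, the LRTI takes the patient out of the harm-free group. It takes the patient out of the benefit group only if it lifts the outcome-year exacerbation count above baseline.

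So the overlap exists on either reading of the review; only its extent changes. Bronchitis behaves the same way only if its codes fall among the lower respiratory codes, which the text does not say. At most 2 of the 8 items are concerned; the other six are not named in the exacerbation definition.

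**Is the benefit term named consistently?** The index describes benefit as fewer severe COPD-related events. Objective 2e uses that label for LRTI and oral thrush. Dataset Variables uses nearly the same label for the adverse events. The operational definition under outcome (3) uses exacerbations. The label thus covers harm in two places and benefit in another.

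**The case against.** The strongest reply is that pneumonia and diabetes are not lost to the study. They are objectives, they are defined variables, and the Statistical Analysis section summarises all outcome variables by device. The adverse-event list is worded openly, and Study Outcomes says that other events will be looked at too. This stands: a reader might infer that the study ignores these harms, and the document does not support that. It does not rescue the index. Dataset Variables places both conditions outside the adverse-event list, so as listed they do not reach the harm term, and open wording leaves the set unfixed.

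Other stronger readings also fail:

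- That every antibiotic-treated LRTI or bronchitis is counted twice. The joint wording of the review and the silence on bronchitis codes prevent that conclusion.
- That benefit and harm cannot be separated at all. Adverse events are listed item by item, Dataset Variables has each exacerbation component analysed separately, and only the index combines the two sides.
- That a fall in oral thrush is scored as benefit because of objective 2e. The operational benefit term is exacerbations; 2e is an inconsistency of wording.
- That calling outcome (1) severe is an error with consequences. The qualifying events are fully specified, so renaming the outcome changes no result.

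It can also be said that the study is exploratory. That lowers the stakes, but the index is one of its named outcomes.

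**Conclusion.** The point holds in two parts. First, the harm term of the therapeutic index rests on an eight-item list with neither pneumonia nor diabetes. Any patient whose only harm is one of these is scored harm-free in the index, though not in the separate summaries. This assumes that the list is applied as written. Second, an LRTI-coded, antibiotic-treated episode can enter both outcome (1) and outcome (2), and through them both terms of the index. How often depends on whether both limbs of the respiratory review are required. Any rate of double counting would rest wholly on assumed exacerbation and LRTI frequencies, so none is given.

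Both parts concern definitions that the protocol itself states and that do not fit together; they are not details that a protocol would normally leave to a later analysis plan. The plan should be changed, but the separate outcome comparisons remain usable without the change.

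**What to change.** 1. Add confirmed pneumonia and new or progressing diabetes, as Dataset Variables already defines them, to the adverse-event set used in outcome (2) and in the harm term of the index. For diabetes the event-type measures are new onset and progression to insulin; the HbA1c and medication-change measures carry no threshold or direction and can stay as separate summaries.
2. Keep LRTI and bronchitis in the item-by-item adverse-event report. Also report the index with a harm term that excludes LRTI and bronchitis episodes already counted as exacerbations, so that the effect of the overlap can be seen. Removing them from harm altogether would be a poorer choice: it would keep only LRTIs that did not meet the exacerbation definition and could hide infection harm.
3. State whether limbs (a) and (b) of the respiratory review are both required, and whether bronchitis codes are lower respiratory codes.
4. Reconcile the label in objective 2e with the exacerbation-based benefit term in outcome (3).

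The cost is protocol wording, a little more derivation work and one extra version of the index. Pneumonia and diabetes are already to be derived, so no new data extraction is needed for them.
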